### **1. Background**

Effectively delivered preconception counseling leads to healthier pregnancy behaviors (1), and high quality contraceptive counseling leads to more effective birth control use (2-4), both of which improve outcomes for women and their offspring (5-7). The Centers for Disease Control and Prevention (CDC) recommend that primary care and reproductive health providers routinely ask reproductive age patients about their personal goals regarding pregnancy and offer preconception and contraceptive counseling guided by the patient's preferences (8). However, only 14% of ambulatory visits by reproductive age women in the United States include any preconception or contraceptive counseling (9). Many clinicians miss opportunities to provide this counseling because they lack tools to identify women who would benefit from it, and may not have the care processes in place to provide appropriate counseling and access to evidence-based care once the need is identified. This need is addressed through our intervention: the One Key Question® (OKQ), a program run through the nonprofit *Power To Decide* to help clinicians efficiently address women's pregnancy intention and provide evidence-based care (Appendix A). Clinicians are trained to ask patients, "Would you like to become pregnant in the next year?" and address contraception and preconception health in a supportive, patient-centered manner. The program provides clinician and staff training, evidence-based clinical tools, and efficient workflows to implement the CDC recommendations (10, 11). We have collected baseline needs assessment data by surveying patients at 6 obstetrics and gynecology and family medicine groups within Northshore University Health Systems (EH 18-015). All 6 of these clinics (see page 3) have agreed to participate in future trainings and post-intervention survey collection at their sites.

### **2. Purpose**

The purpose of this pilot study is to build upon baseline data on pregnancy intention and receipt of contraceptive and preconception counseling. 2 of the 4 participating practices will be randomly selected to receive comprehensive One Key Question® training through the nonprofit *Power To Decide*. All trained sites also have access to technical support in implementing OKQ. This training and technical support will act as the intervention and be given to help improve the quality of preconception and contraceptive counseling in Primary care and Obstetrics/Gynecology. All participating practices will then be surveyed again to determine changes in contraception and preconception counseling. Following this second round of surveys, the remaining practices will have the option to receive *Power To Decide*'s One Key Question ® training.

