### **3. Methodology**

#### **Part I: Trainings**

- a. 2 of the 4 participating NorthShore Medical Groups will be selected to receive *Power To Decide* OKQ trainings. These become the *intervention practices* and the remaining 2 become *control practices*. The selection of these sites will be determined based on site availability, willingness to participate, and clinic characteristics.
- b. Trainings will be provided to clinicians and staff from the intervention practices.
- c. Trainers from *Power To Decide* will execute OKQ trainings
- d. Trainings consist of:
  - Up to seven hours of training, in-person certification training (Appendix B)
  - Provider and Patient Materials
  - Five hours of consulting (prior to and following training)
  - Post training webinar
  - Provider OKQ Certification (two years for the price of one)
  - Access to a OKQ Provider Portal (only available to certified providers)

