**7. Type and number of experimental subjects**

Up to 100 clinicians and staff that take part in the OKQ Training. Up to 234 patients from OB and FM clinics will be approached for to be surveyed.

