**8. Statistical analysis**

A simple frequency and chi square analysis will be used to describe outcomes at each time point: baseline and post-OKQ.

To compare the effect of OKQ on preconception and contraceptive counseling, a difference-in-differences analysis will be conducted, comparing change in rate of counseling at the intervention practices vs. at the control practices.

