One Key Question: Pilot Study at NorthShore

Statistical Analysis Plan

Clinicaltrials.gov (NCT03947788)

11/17/2020

Patients were excluded from analysis if they reported experiencing menopause or having a hysterectomy or sterilization. Since OKQ is a practice-level intervention, we used intention-to-treat analysis and calculated each practice's rate for each outcome, regardless of whether patients' individual physician had participated in the OKQ training. In each group of patients (baseline time point in control and intervention practices, and post-intervention time point in control and intervention practices), we calculated the percentage receiving reproductive counseling and the percentage who were extremely or very satisfied.

We used chi square tests to compare rates across the two time points within each practice. We also used multivariable logistic regression with an intervention time point interaction (difference-in-differences) term to assess intervention efficacy independent of differences across sites and time trends unrelated to the intervention, controlling for practice type (ob/gyn vs. primary care), patient age, race/ethnicity, and reason for visit. Results are reported as adjusted odds ratios (aOR) and 95% confidence intervals (CI). All analyses were conducted using SAS 9.4 (SAS Inc., Cary, NC).

We calculated a minimum sample size of 260 was needed to observe a 15% between-group difference in the pre-to-post change in counseling rates with 80% power. The statistical significance level for all tests was <0.05.

This research was registered on clinicaltrials.gov (NCT03947788) and approved by NSUHS Institutional Review Board (IRB). Analysis of de-identified data was exempted by the University of Chicago IRB (The University of Chicago, 19-0149; NSUHS, 18-343).

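### Neither selection rule balances the arms on ob/gyn versus family medicine, and the SAP model has no practice type × time term, so a specialty-specific change over time can enter the OKQ estimate

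*Protocol*

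**What the plan says.** The protocol gives two rules for choosing the intervention practices. Section 2 (Purpose) says "2 of the 4 participating practices will be randomly selected to receive comprehensive One Key Question® training". Section 3, Part I, item a, says "The selection of these sites will be determined based on site availability, willingness to participate, and clinic characteristics". Neither mentions pairing, stratifying or balancing by specialty.

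Both specialties are in the study. The baseline work involved "surveying patients at 6 obstetrics and gynecology and family medicine groups within Northshore University Health Systems" (section 1), and for the post-training round "Up to 234 patients from OB and FM clinics will be approached" (section 7).

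The protocol's effect analysis (section 8) is a difference-in-differences, "comparing change in rate of counseling at the intervention practices vs. at the control practices". The SAP carries this out as "multivariable logistic regression with an intervention time point interaction (difference-in-differences) term", "controlling for practice type (ob/gyn vs. primary care), patient age, race/ethnicity, and reason for visit". Practice type is listed as a covariate, and no interaction of practice type with time is stated. The SAP says the purpose of the model is "to assess intervention efficacy independent of differences across sites and time trends unrelated to the intervention".

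**The concern.** A difference-in-differences cancels any fixed difference between practices. It does not cancel a difference in how practices change between the two surveys. If counselling in ob/gyn and in family medicine moves differently for reasons unrelated to OKQ, and the arms differ in specialty mix, part or all of that movement is counted as an OKQ effect. A main effect for practice type cannot prevent this, because it too describes a fixed difference.

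The SAP's statement that efficacy is assessed independently of unrelated time trends therefore depends on how specialties fall across the arms. Neither document fixes that. With four practices the imbalance can be complete.

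**Working it through.** **1. The plan's own figure, for scale.** The SAP gives N = 260 for a 15% difference at 80% power. Assume 14% counselled (the national figure in protocol section 1, not stated to be the input), 29% as the alternative, and two-sided 5%.

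- Uncorrected n per group = [1.96·√(2·0.215·0.785) + 0.8416·√(0.14·0.86 + 0.29·0.71)]² / 0.15² = 116.6, so 117 per group and 234 in total.
- With the continuity correction, n′ = (116.6/4)·[1 + √(1 + 4/(116.6·0.15))]² = 129.6, so 130 per group and 260 in total.

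The figure is reproduced. It is used here only for survey numbers: 260 over 4 practices and 2 time points is 32.5, taken as 33 per practice per time point. Reading 234 as one survey round gives 234/4 = 58.5, taken as 58.

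**2. Allocations.** Choosing 2 of 4 gives C(4,2) = 6 allocations.

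| Specialty split | Arm identical to specialty | Arms balanced on specialty |
|---|---|---|
| 2:2 | 2 of 6 (33%) | 4 of 6 |
| 3:1 or 1:3 | 0 of 6 | 0 of 6 |
| all one type | 0 of 6 | 6 of 6 |

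These proportions are probabilities only under the unconstrained random draw of section 2. Under Part I, item a, no probability can be calculated.

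**3. What enters the estimate.** On the percentage-point scale, with equal patient numbers per practice, the change in practice i is

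change_i = common trend + OKQ × arm_i + d × ob/gyn_i,

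where d is the extra change in ob/gyn unrelated to OKQ. A practice-type main effect is the same at both time points and drops out of the change. Hence

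bias = d × (ob/gyn share of intervention practices − ob/gyn share of control practices).

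- Arm identical to specialty: d × (1 − 0) = d in size. With an assumed d of 5 points, that is 5/15, one third of the target.
- One practice of each type per arm: d × (½ − ½) = 0.
- 3:1 split: d × (1 − ½) or d × (½ − 1), which is d/2 in either direction.

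**4. Can the model repair it?** If arm equals specialty, the SAP's design (intercept, arm, time, arm × time, practice type) has rank 4 with 5 columns, so practice type duplicates arm. Adding practice type × time gives 6 columns, still rank 4, and the OKQ effect is not estimable. With a 3:1 split, or a 2:2 split balanced across arms, adding that term gives full rank, 6 of 6.

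**5. Odds-ratio scale, no OKQ effect.** Assumed baselines are 40% in ob/gyn and 30% in family medicine, with change in ob/gyn only, when both intervention practices are ob/gyn and both controls family medicine. For d = 15 points the expected interaction odds ratio is (0.55/0.45)/(0.40/0.60) = 1.83. Simulation with 1,000 data sets per scenario, without the patient-level covariates, gave:

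| d (points) | Median OR, 33 per cell | Rejection, 33 per cell | Rejection, 58 per cell |
|---|---|---|---|
| 5 | 1.28 | 7% | 10% |
| 10 | 1.45 | 15% | 18% |
| 15 | 1.87 | 24% | 34% |
| 20 | 2.22 | 34% | 55% |

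With one practice of each type per arm, the median odds ratio was about 1.0 and rejection 4 to 6%. With a 3:1 split, d = 15 and the single family medicine practice in the control arm, the median odds ratio was 1.37 under the SAP model and 1.00 once practice type × time was added.

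**The case against.** The strongest reply is that the damaging case rests on facts the documents do not supply.

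- **The split.** Arm can equal specialty only with a 2:2 split. The protocol's Background points to a list of clinics that is not in the text available here, so the split must be treated as unknown and not as an omission. This stands.
- **The selection rule.** The 33% applies to section 2 only. Specialty is an obvious clinic characteristic, so Part I, item a, may have been meant to allow balancing. It may, but it does not say so. A specialty constraint is neither shown nor excluded.
- **The SAP's wording.** It is dated 11/17/2020, is written in the past tense, and reports practice type as a covariate beside the intervention × time term. Under full aliasing that covariate would do nothing. This suggests, without proving, that full aliasing did not occur.
- **Other adjustment.** The model also includes age, race or ethnicity and the reason for the visit, so a trend acting through case mix would be partly absorbed. The within-practice chi-square tests would also show practice-level changes. Both points stand and make the bias in the working an upper figure for such trends.
- **Size.** No document gives a specialty difference in trend. At 5 points, even full confounding raises rejection only to 7 to 10%.

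Two stronger readings are tempting. A reader might infer that this trial carried a one-in-three chance of full confounding, or that its arms were in fact split by specialty. The documents support neither, for the first three reasons above. A reader might also infer that the SAP regards practice type as the main difference between sites. It lists it as one covariate among four.

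**Conclusion.** The point holds as a gap in the design rule and the model. No stated rule balances the arms on specialty, and the stated model does not remove a specialty-specific change over time. This is separate from whether selection was random, since a properly random unconstrained draw leaves the same gap.

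The size is conditional. With a 2:2 split and an unconstrained draw, 2 of 6 allocations alias arm with specialty, and the whole of any specialty-specific trend not explained by the patient covariates goes into the OKQ estimate. With a 3:1 split no allocation is fully aliased, but none is balanced, and about half of such a trend enters. With all four practices of one type, or a 2:2 split balanced across arms with similar patient numbers, the problem disappears. The trend sizes and baseline rates in the working are assumptions.

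The change is worth making because it costs little, and because the SAP's claim about time trends is unconditional while its validity depends on the allocation.

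**What to change.** 1. **Selection rule.** Reconcile protocol section 2 with section 3, Part I, item a, into one rule: list the four practices with their type, pair them by type, and draw one practice at random from each pair. With a 3:1 split, state the type of each practice by arm and name the type that cannot be balanced.
2. **Model.** Add practice type × time to the SAP's logistic model, or report the change by specialty, wherever these can be estimated.
3. **If selection is already done.** Report each practice's type by arm. If arm equals specialty, withdraw the claim that the model works "to assess intervention efficacy independent of differences across sites and time trends unrelated to the intervention". If the arms are only partly unbalanced, apply item 2.

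**Cost.** With a 2:2 split, pairing reduces the possible allocations from 6 to 2 × 2 = 4, none of them fully confounded, and leaves less scope for site availability. It needs no extra patients, training or surveys.

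The added term costs almost no precision when each arm has one practice of each type. With a 3:1 split it costs more, because the single practice of its type no longer informs the OKQ effect. With equal numbers per practice, the variance factor rises from ½ + ½ = 1 to ½ + 1 = 1.5, so the standard error grows by √1.5, about 1.2 times.

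**What remains.** With two practices per arm, any other practice-specific change over time stays confounded with OKQ. Pairing by type does not remove that, and the report should say so.

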### **3. Methodology**

#### **Part I: Trainings**

- a. 2 of the 4 participating NorthShore Medical Groups will be selected to receive *Power To Decide* OKQ trainings. These become the *intervention practices* and the remaining 2 become *control practices*. The selection of these sites will be determined based on site availability, willingness to participate, and clinic characteristics.
- b. Trainings will be provided to clinicians and staff from the intervention practices.
- c. Trainers from *Power To Decide* will execute OKQ trainings
- d. Trainings consist of:
  - Up to seven hours of training, in-person certification training (Appendix B)
  - Provider and Patient Materials
  - Five hours of consulting (prior to and following training)
  - Post training webinar
  - Provider OKQ Certification (two years for the price of one)
  - Access to a OKQ Provider Portal (only available to certified providers)

### **Part II: Survey Collection – Starts at least 4 weeks after OKQ Training**

- a. The research team will work with physicians and practice managers at all participating NorthShore practices to select mutually agreeable days for data collection at each site.
- b. On data collection days, patient surveys will proceed using the same procedures as those used for baseline data (EH 18-015). Specifically:
  1. A research assistant (RA) will approach a patient in the waiting room before her appointment. After verbal recruitment and consent, the RA will determine if she qualifies for the study.
  2. If the patient is eligible, the RA will explain the study and ask that she comes back to the waiting room after her appointment to fill out a post-exam survey. The RA will instruct the participant to place completed survey in an envelope.
  3. The RA will collect the survey and offer a \$10 Walgreens or CVS gift card as a token of appreciation for participating in the study.
- c. After patient data collection is complete, the RA will return to each practice to collect surveys from clinicians and staff (Appendix C) at the intervention practices to assess the experience of implementing OKQ and their perceptions of its utility for patients.
  1. OKQ staff will attend clinic staff meetings at intervention practices to introduce the survey in-person in order to increase buy-in among respondents.
  2. Clinicians and staff will receive the survey through an emailed link as well as in paper form:
    - i. A paper survey with a cover letter (Appendix F) attached will act as our consenting process. This cover letter will also include a link to the online version of the survey if they choose to complete the survey online.
    - ii. All clinician and staff will receive an email that includes a copy of the cover letter and a link to the survey online.
  3. All individuals taking these surveys on paper forms will be asked to leave their completed surveys at their clinic in a secure location for the RA to pick up.

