**12. Procedures to obtain and record informed consent**

- a. While in the waiting room, a researcher will approach a patient who appears to be 18-49, non-pregnant, and female after the patient checks in for her appointment.
- b. The researcher will read the oral recruitment and consent script. The patient has to agree to hear more about the study (after oral recruitment), provide verbal consent, and meet study criteria in order to participate. A one page information sheet (Appendix G) about the study and their rights

as a participant will be given while verbally consenting and if desired patients can take the one pager home to keep. See **Part II: Survey Collection** for more details on the overall recruitment and consenting process.

- c. An information sheet cover letter explaining the study (Appendix F) will be included in both the paper version and electronic version of the survey provided to clinicians and staff. The cover letter will be in the body of the email which contains the link to the survey. The link will be listed after the cover letter. Please see section **Part II: Survey Collection subsection c** for more information.

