### **15. Recruiting methods**

- a. RA will approach female patients in waiting room that appear to be w/in study age range and not pregnant

- b. The RA will ask (following the oral recruitment/consent script) if the patient would like to participate in the study
- c. The patient will be seen by the provider
- d. The patient will then return and approach the RA to complete the survey
- e. As for clinician and staff recruitment, research staff will attend clinic staff meetings at intervention practices to introduce the survey in-person in order to increase buy-in among respondents. For more details see section **Part II: Survey Collection subsection c.2.**

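### Post-training survey days are agreed with physicians and managers who know their arm, so a lean toward trained clinicians would enter the difference-in-differences as an OKQ effect

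*Protocol*

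**What the plan says.** Protocol section 3, Part II, item a sets the survey days. The study's researchers are to "work with physicians and practice managers at all participating NorthShore practices to select mutually agreeable days for data collection at each site". The heading of Part II places this after the intervention: "Starts at least 4 weeks after OKQ Training".

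Part I, item b describes who is trained: "Trainings will be provided to clinicians and staff from the intervention practices". It sets no minimum coverage. The SAP calculates each practice's rate "regardless of whether patients' individual physician had participated in the OKQ training" and calls this intention-to-treat. It therefore allows trained and untrained physicians to work side by side in an intervention practice.

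Part II, item b says that surveys on collection days follow the baseline procedure. That statement covers conduct on the day. Item a, on choosing the days, carries no such statement. Section 12 says that "a researcher will approach a patient who appears to be 18-49, non-pregnant, and female after the patient checks in for her appointment". Item b then has the research assistant check eligibility, and section 15 adds: "The patient will then return and approach the RA to complete the survey".

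The SAP's logistic model adjusts for practice type, age, race/ethnicity and reason for visit. It does not adjust for clinician, clinician training status or survey session.

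**The concern.** A practice's rate is measured without bias only if the surveyed sessions represent the practice's visits. Here the sessions are settled after allocation, with input from people who went through the training or manage those who did. No blinding is described, and an in-person programme of up to seven hours could hardly be concealed from them. Days could come to favour clinicians who were trained for quite innocent reasons, such as trained clinicians being the ones most willing to host the survey.

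At baseline no clinician had yet been trained in this study, and control practices have none at either wave. A lean of this kind would therefore arise in one of the four cells only. A difference-in-differences removes what is common to both waves or both arms. It does not remove something confined to the post-training intervention cell, because that is exactly where it looks for the effect. What is at stake is whether the reported effect belongs to the practice or to the sessions that happened to be surveyed.

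**Working it through.** **Plan's own figure.** The documents give no figure for training coverage or for the clinician mix surveyed, so there is nothing on this point to reproduce. I take the SAP's 15% target difference, read as percentage points, as the true practice effect. All shares below are assumptions.

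**Set-up.** For an intervention practice, let
- s = true share of eligible visits that are with trained clinicians;
- s′ = that share among the women surveyed after training;
- d_T, d_U = change in counselling rate among trained and untrained clinicians, net of the control change;
- g = baseline rate of the clinicians later trained minus that of the others.

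Assume the baseline wave sampled clinicians in proportion to their visits. Then

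- true practice effect = s·d_T + (1 − s)·d_U
- estimate = s′·d_T + (1 − s′)·d_U + (s′ − s)·g
- bias = (s′ − s) × [(d_T − d_U) + g]

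The arithmetic is on the percentage-point scale. The SAP's model reports an odds ratio, but the same cell shift feeds its interaction term.

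**Case 1: no change among untrained clinicians (d_U = 0), no prior gap (g = 0), true effect 15 points.** Then d_T = 15/s and the estimate is 15 × s′/s.

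| True share s | Sampled share s′ | Estimate (points) | Bias (points) |
|---|---|---|---|
| 100% | 100% | 15 × 1.00/1.00 = 15.0 | 0 |
| 90% | 100% | 15 × 1.00/0.90 = 16.7 | +1.7 (11%) |
| 70% | 90% | 15 × 0.90/0.70 = 19.3 | +4.3 (29%) |
| 50% | 60% | 15 × 0.60/0.50 = 18.0 | +3.0 (20%) |
| 50% | 75% | 15 × 0.75/0.50 = 22.5 | +7.5 (50%) |

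At full coverage there is no untrained clinician to leave out, so the bias is zero. At 90% coverage the 11% shown is the maximum under these assumptions. Days that lean away from trained clinicians bias the estimate downward by the same formula.

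**Case 2: spillover.** Suppose coverage is 50%, trained clinicians gain 30 points and untrained colleagues gain 15. The true effect is 0.5 × 30 + 0.5 × 15 = 22.5.
- s′ = 75%: 0.75 × 30 + 0.25 × 15 = 26.25, which is 17% too large (50% without spillover).
- s′ = 60%: 0.60 × 30 + 0.40 × 15 = 24, which is 7% too large (20% without spillover).

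**Case 3: training has no effect (d_T = d_U = 0).** The bias is (s′ − s) × g. It is zero unless the trained clinicians already counselled at a different rate. A 20-point shift in mix with a 10-point gap gives 0.20 × 10 = 2 points. A 30-point shift with a 20-point gap gives 0.30 × 20 = 6 points.

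**The case against.** **Agreeing days with clinics is ordinary logistics in a four-practice pilot.** No text suggests steering, and convenience could move the mix either way. This stands as a limit on the claim: the documents leave room for a bias but do not show one.

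**Coverage may be near complete.** The protocol offers training to clinicians and staff and allows for up to 100 of them, and the SAP's wording permits gaps without saying how large. OKQ also brings staff training, tools and workflows, so untrained clinicians may improve too. Both points stand, and both shrink the bias, as cases 1 and 2 show.

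**Intention-to-treat and the unchanged baseline procedure might be thought to settle it.** They do not. Intention-to-treat governs how surveyed women are analysed, not which women are surveyed. The baseline statement covers procedures on the day. Even if days were also chosen in the same way at baseline, there were no study-trained clinicians then to favour.

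**A reader might infer that approaching women by appearance over-represents trained clinicians.** The documents do not support this. Appearance is a pre-screen for age, sex and pregnancy, followed by an eligibility check. It is applied in every cell and has no stated link to the clinician's training, so it should largely cancel. Likewise, the need to return after the visit applies in all four cells, and nothing shows that return differs between them.

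**An absence cannot be fully proved.** The text between Part II and section 5, the appendices and the baseline protocol (EH 18-015) were not available. I can say only that the available text contains no rule for random or pre-set sessions, consecutive approach or a recruitment log.

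**Conclusion.** The point holds in a limited form. The rule in Part II, item a allows the clinician mix to shift in the post-training intervention cell alone, and neither the design nor the model would remove that shift. Whether it happened, and in which direction, cannot be told from the documents.

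For a true effect of 15 points, the illustrated estimates run from 15 (no bias) to 22.5 points. The upper figure needs 50% coverage, a sampled share of 75% and no gain at all among untrained clinicians. It would be wrong to read it as a finding that the trial's effect is inflated by half. This is a cheap improvement to the sampling rule, not a demonstrated error in the result.

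**What to change.** **Item a.** Have the research team draw survey sessions at random from each practice's clinic schedule, so that clinicians are covered in proportion to their visits. A practice may veto a drawn session for logistical reasons only.

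**Item b.** Keep the existing pre-screen and approach the women who pass it in order of check-in.

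**Tally.** Keep an identifier-free count by practice, wave and session of women approached, eligible, consented and returned, noting whether the session's clinician was trained. Training status is essential, because a tally by practice and wave alone could not reveal this bias. Report the tally alongside the difference-in-differences. The protocol says baseline data are already collected, so for that wave report whatever was recorded.

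**If collection is complete.** The SAP is written in the past tense, so the sampling change may be too late for this round. In that case report survey days and clinician mix in each of the four cells where they were recorded. Where they were not, state the limitation.

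**Cost.** Revised wording, a short tally sheet and slightly less convenient scheduling for the practices. Keeping the pre-screen avoids approaching many women who are plainly ineligible.
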